#### **4.5.2. Interruption of Enrollment/Trial Cessation**

Section 4.5.1 describes the circumstances for potential withholding or reduction of drug treatment in individual patients. This section lists events that will necessitate interruption of enrollment in the trial as a whole, pending DSMB review. As part of their ongoing safety review, the DSMB will make independent judgments regarding other adverse events requiring trial interruption.

1. Any death that occurs in the study which is assessed as possibly, probably, or definitely related to study treatment regimen by the study site investigator and the medical monitor.
2. Two or more of the first 10 treated participants or  $\geq 20\%$  of all treated participants experience a clinically significant, drug-related adverse event, resulting in the permanent discontinuation of study treatment.
3. If more than one of the first 10 treated participants or  $\geq 10\%$  of all treated participants develop clinically significant retinal changes, the study will be placed on hold pending review by DSMB.

### **5. STUDY VISIT ASSESSMENTS**

The schedule of evaluations and laboratory studies is presented in Appendix 2, Schedule of

Assessments. A summary of assessments for the Protocol is given below.

### **5.1. General Assessments**

General assessments for this Protocol will include:

- Informed consent
- Inclusion/exclusion criteria
- Medical history
- Complete or directed physical examination including height/weight, waist circumference and Tanner staging
- Concomitant medications
- Adverse events
- Treatment compliance
- Ophthalmology examination

### **5.2. Laboratory Assessments**

The following clinical laboratory assessments will be performed during the study as described in the Schedule of Assessments:

- Chemistry (sodium, potassium, chloride, CO2, glucose, BUN, creatinine)
- Liver function tests (ALT, AST, LDH, alkaline phosphatase, total protein, albumin, total and direct bilirubin)
- Hematology (CBC with differential and platelets)
- Urine pregnancy test as appropriate
- Antibodies to HIV, hepatitis B (anti-HBcAb, HBsAg), hepatitis C (HCV)
- G6PD screening

### **5.3. Mechanistic Outcome Assessments**

TrialNet will perform pharmacokinetic, immune, and genetic assays to further understand mechanisms that may be underlying the T1D disease process and response to therapy. For this purpose, samples for PBMC, DNA, RNA, plasma, and serum may be obtained. Islet autoantibodies will be measured at approximately six-month intervals in the study. HLA or other testing for diabetes-related genes may be done under the auspices of either the TrialNet Pathway to Prevention Study or this protocol.

Responses to influenza or other clinically indicated immunizations may be determined through analysis of pre- and post-dose samples. Samples may also be collected for thyroid autoantibodies, virology and other immunization titers. Details of the mechanistic outcome assessments can be found in the mechanistic analysis plan.

## 5.4. Metabolic Outcome Assessments

Metabolic assessments will consist of:

1. OGTT
  - The OGTT will be performed approximately every 6 months, or more frequently if clinically indicated based on a random glucose level of  $\geq 200$  mg/dL (11.1 mmol/L).
  - The C-peptide and insulin data from the OGTT will be used to determine insulin secretion with assessment of early and late insulin responses.
  - The insulin, glucose and C-peptide data from the OGTT may be used to determine insulin sensitivity.
  - Other hormones and metabolites such as glucagon and proinsulin may also be measured.
2. HbA1c
  - Measure of glycemic control.

## 5.5. Visit Windows

Randomization must occur within 7 weeks (no more than 52 days) of the OGTT, and initial treatment administration must begin no more than 4 weeks after randomization. Visit target dates will be determined as of the baseline visit and will not be changed. Subsequent study visits should be +/- 2 weeks of the target date.

## 6. ADVERSE EVENT REPORTING AND SAFETY MONITORING

### 6.1. Adverse Event Definition

#### 6.1.1. Adverse Event

In this clinical trial, an adverse event (AE) is any occurrence or worsening of an undesirable or unintended sign, symptom or disease, whether or not related to the treatment and study procedures.

Throughout the study, the investigator must maintain source documentation of all adverse events. Events *not related to diabetes onset* which are Grade 2 or greater per the NCI CTCAE (see Section 6.1.5. Grading Event Severity below) must be reported to TNCC. The investigator should treat participants with adverse events appropriately and observe them at suitable intervals until the events resolve or stabilize.

Adverse events may be discovered through:

- observation of the participant;
- questioning the participant;
- unsolicited complaint by the participant.

Questioning of the participant should be conducted in an objective manner.

### 6.1.2. Adverse Reaction

An adverse reaction means any adverse event caused by a drug. Since diabetes onset is a study endpoint, this is not considered an adverse reaction unless associated with death. Adverse reactions are a subset of all suspected adverse events for which there is reason to conclude that the drug caused the event. Suspected adverse reaction means any adverse event for which there is a reasonable possibility that the drug caused the adverse event. For the purposes of safety reporting, “reasonable possibility” means there is evidence to suggest a causal relationship between the drug and the adverse event. A suspected adverse reaction implies a lesser degree of certainty about causality than an adverse reaction, which means any adverse event definitely caused by a drug. Examples of evidence that suggest a causal relationship (reasonable possibility) between the drug and the adverse event include:

- A single occurrence of an event that is uncommon and known to be strongly associated with drug exposure.
- One or more occurrences of an event that is not commonly associated with drug exposure, but is otherwise uncommon in the populations exposed to the drug.
- An aggregate analysis of specific events observed in a clinical trial (such as known consequences of the underlying disease or condition under investigation or other events that commonly occur in the study population independent of drug therapy) that indicates those events occur more frequently in the drug treatment group than in a concurrent or historical control group.

### 6.1.3. Serious Adverse Event/Reaction

A serious adverse event (SAE) or reaction is defined as any untoward medical occurrence at any dose that suggests a significant hazard, contraindication, side effect, or precaution. This includes but is not limited to any of the following events with the *exception of an adverse event associated with, the initial diagnosis of type 1 diabetes including hospitalization related to that diagnosis. In the event that a DKA related hospital admission occurs, all relevant details of the admission should be reported to the TNCC. The diagnosis of diabetes will be reported as an SAE only in the event of death.*

1. Death. A death that occurs during the study or that comes to the attention of the investigator during the protocol-defined follow-up after the completion of therapy must be reported whether it is considered to be treatment-related or not.
2. A life-threatening adverse event. A life-threatening event is any adverse event that, in the view of the investigator, places the participant at immediate risk of death from the reaction as it occurred.
3. Inpatient hospitalization or prolongation of existing hospitalization, with the exception of hospitalization relating to initial diagnosis of type 1 diabetes.
4. Persistent or significant incapacity or substantial disruption of the ability to conduct normal life functions.
5. Congenital anomaly or birth defect.
6. Important medical events that may not result in death, be life-threatening, or require hospitalization may be considered serious when, based upon appropriate medical

judgment, they may jeopardize the participant and may require medical or surgical intervention to prevent one of the outcomes listed above.

An adverse event or suspected adverse reaction is considered “life-threatening” if, in the view of either the investigator or sponsor, its occurrence places the participant at immediate risk of death. It does not include an adverse event or suspected adverse reaction that, had it occurred in a more severe form, might have caused death.

Regardless of the relationship of the adverse event to study drug, the event must be reported as a serious adverse event if it meets any of the above definitions.

#### **6.1.4. Unexpected Adverse Event/Reaction**

An adverse event/reaction is considered unexpected when the nature (specificity) or severity of the event is not consistent with the risks described in the package insert, this protocol, or the informed consent document. Unexpected refers to an experience that has not been previously observed. This includes events that occur more frequently than expected.

#### **6.1.5. Grading Event Severity and Causality**

TrialNet has adopted usage of the National Cancer Institute (NCI) Common Terminology Criteria for Adverse Events (CTCAE) and/or study-specific criteria for classification to describe the severity of adverse events *with the exception of hypoglycemia, hyperglycemia or diabetes onset* (which will be reported as an AE only in the case of death). TrialNet Investigators will also provide an assessment of relationship of AE to study drug as: not, unlikely, possibly, probably, or definitely related.

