Importantly, the drug not only has been shown to ameliorate other autoimmune diseases, but hydroxychloroquine also abrogates the progression of autoimmunity in at-risk populations. This drug is therefore particularly suitable to test early in the T1D process, in this study, targeting those with multiple islet autoantibodies but normal glucose tolerance (Stage 1 of T1D). It also has the potential to be efficacious at an even earlier stage of the disease process, prior to the development of multiple autoantibodies.

Initially developed as a therapy for malaria, hydroxychloroquine is approved by the Food and Drug Administration (FDA) and the European Medicines Agency (EMA) for that indication, as well as for rheumatoid arthritis (RA) and discoid and systemic lupus erythematosus (SLE). It is widely used in

clinical practice for these indications, including in pediatric populations. Efficacy in autoimmune disease has been well established in RA, SLE, antiphospholipid syndrome and Sjögren’s syndrome. Particularly relevant for this study is that hydroxychloroquine is effective when used early in the course of autoimmune disease, having been shown to slow or halt progression in palindromic rheumatism and delay onset of SLE in antibody-positive individuals.

Other beneficial actions of hydroxychloroquine have been identified in epidemiologic and randomized studies of other autoimmune diseases, including improvement in cardiovascular risk factors, such as reduction of LDL cholesterol, thrombosis, glycaemia, insulin resistance, and reduction of risk of incident diabetes mellitus in SLE and RA. A randomized trial of hydroxychloroquine in obese adults demonstrated improved clamp-assessed insulin sensitivity, as well as increased first phase insulin secretion, possibly mediated through anti-inflammatory effects. Because 1/3rd of our pediatric population is currently overweight, and elevated BMI may increase risk of progression to T1D in children and adults, these actions may provide an additional benefit to this therapy.

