### **6.2. Adverse Event Reporting and Monitoring**

Adverse events will be reported to the TrialNet Coordinating Center. The investigator will grade their severity according to common toxicity criteria or study-specific criteria and will make a determination of their relation to therapy *with the exception of the initial diagnosis of diabetes which is considered an adverse event only in the case of death*. Events will be assessed and reported consistent with the ICH Guideline for Good Clinical Practice, 21 CFR 312.32 for expedited safety reporting, and per the guidance of the DHHS Office for Human Research Protections (OHRP).

The adverse event case report form for the protocol must be completed for all AEs  $\geq$  Grade 2. In addition to the reporting requirements for the TrialNet network (as described above), the FDA requires reporting of any adverse event, if the event is serious, related, AND unexpected (21CFR312.32 (c)(i)(A)-(B)). When required, the FDA form 3500A (MedWatch form) should also be completed and sent to the TNCC *within 24 hours of when the site was notified of the event*. This will be reviewed by the TrialNet Medical Monitor, the TrialNet Safety Monitoring Committee, and the DSMB, as appropriate. Deaths must be reported immediately. Event outcome and other follow-up information regarding the treatment and resolution of the event will be obtained and reported when available, if not known at the time the event is initially reported. The follow-up information should contain sufficient detail to allow for a complete medical assessment of the case and an independent determination of possible causality.

Adverse events will be assessed by the TrialNet Medical Monitor. The DSMB will conduct regular safety reviews approximately every three to six months (and otherwise as needed) of adverse events by treatment group assignment. Serious adverse events, as well as adverse events leading to study discontinuation, will be reviewed by the DSMB.

For SAEs that are unexpected and considered possibly or probably drug-related, the Medical Monitor will provide information on frequency of similar events, and will review FDA form 3500A reports for distribution to FDA (and equivalent regulatory bodies for non-US sites), NIDDK, DSMB, and site investigators. Expedited safety reports will be submitted to the IND by the TNCC on behalf of NIDDK.

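### Protocol 6.1.5 exempts hypoglycemia and hyperglycemia from severity grading while 6.1.1 and 6.2 do not, so non-serious hypoglycemia may be counted at some sites and not at others.

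*Protocol*

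**What the plan says.** Four sections of the Protocol govern which events are graded and reported, and their exceptions differ.

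- Section 6.1.5 adopts CTCAE and/or study-specific criteria for severity "with the exception of hypoglycemia, hyperglycemia or diabetes onset", followed in parentheses by "which will be reported as an AE only in the case of death".
- Section 6.1.1 confines reporting to events "not related to diabetes onset" and sets the trigger as events "which are Grade 2 or greater per the NCI CTCAE (see Section 6.1.5. Grading Event Severity below) must be reported to TNCC".
- Section 6.2 has the investigator grade severity and judge relation to therapy "with the exception of the initial diagnosis of diabetes which is considered an adverse event only in the case of death". It requires the adverse event form for every event of Grade 2 or above.
- Section 6.1.3 excepts from serious adverse events only those tied to the initial diagnosis of type 1 diabetes. For the rest it says: "Regardless of the relationship of the adverse event to study drug, the event must be reported as a serious adverse event" if any of its definitions is met.

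The analyses depend on grade. Protocol 8.3 records the maximum grade of each toxicity per participant. SAP section 8 states that only Grade 2 or greater events were reported, and it compares the highest grade per subject between arms.

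**The concern.** Exempting hypoglycemia from adverse event grading makes sense where participants take insulin and low glucose is background disease. That does not describe this trial. Participants enter with normal glucose tolerance, a history of insulin or other diabetes therapy is an exclusion (Protocol 3.3.2), and follow-up under this protocol ends at Stage 3 (Protocol 3.9.2).

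The rationale also credits the drug with metabolic effects in the relevant direction. Section 2.2.1 cites a trial in obese adults that "demonstrated improved clamp-assessed insulin sensitivity, as well as increased first phase insulin secretion", and section 2.2.1.2 cites improved glycemic control in adults with type 2 diabetes. Hypoglycemia is therefore a plausible event to watch for.

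Comparing safety and tolerability with placebo is a stated secondary objective (Protocol 3.2.2). If collection depends on which section a site follows, a count of hypoglycemia has no clear meaning, and a zero could look like reassurance when it reflects non-collection.

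**Working it through.** No figure in the plan bears on this point, and no arithmetic applies. The check is to set the sections side by side and follow specific cases through them.

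**How an event reaches the data.** Section 6.1.1 requires reporting at Grade 2 or above and refers to 6.1.5 for the grade. Sections 6.2 and 10.3 use the same threshold. SAP section 8 works from events that passed it. An event without a grade cannot meet the trigger. The exception in 6.1.5 covers both CTCAE and study-specific criteria, and the documents give no separate scale for hypoglycemia.

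**Two readings of the death clause.** The parenthesis in 6.1.5 can attach to all three listed conditions (broad reading) or to diabetes onset alone (narrow reading). Sections 6.1.2, 6.1.3 and 6.2 each tie their death clause to diabetes onset or diagnosis, which favors the narrow reading. The grammar does not settle it.

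**Case 1: non-serious hypoglycemia that would be Grade 2.**
- Under 6.1.1 and 6.2: graded and reported, because it is neither diabetes onset nor its initial diagnosis.
- Under 6.1.5, broad reading: not graded, and not reported unless fatal.
- Under 6.1.5, narrow reading: still not graded, so the Grade 2 trigger is never met.
- Result: a conflict on both readings.

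**Case 2: hospitalization for hypoglycemia unrelated to the initial diagnosis.**
- Under 6.1.3: a serious adverse event, defined without reference to grade.
- Under 6.1.5, broad reading: not an adverse event unless fatal, which contradicts 6.1.3.
- Under 6.1.5, narrow reading: no conflict over reporting, although the event carries no severity grade.

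**Case 3: hyperglycemia that is not part of diabetes onset.**
- The same mismatch as Case 1 arises between 6.1.5 and 6.2.
- There is a complication. Abnormal glucose tolerance is part of the primary endpoint (Protocol 8.1), including values of at least 200 mg/dL at 30, 60 or 90 minutes. These values are not the initial diagnosis of diabetes, so the wording of 6.2 does not clearly exempt them.

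**Case 4: diabetes onset.**
- The four sections are compatible: outside the case of death, it is not handled as an adverse event.

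The conflict is therefore confined to hypoglycemia and to hyperglycemia outside diabetes onset. For non-serious events it survives the more charitable reading.

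**The case against.** The strongest reply is that this is a drafting slip with limited reach, and much of that stands.

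A reader might infer that non-fatal hypoglycemia would disappear from the tables, the withholding rules and the DSMB's review altogether. The documents do not support that. Hospitalized, life-threatening or medically important cases meet 6.1.3. Under 6.2 the DSMB reviews serious adverse events and events leading to study discontinuation. SAP section 8 tabulates serious events and events leading to discontinuation of study drug. Item 5 of the withholding list in 4.5.1 is triggered by a related serious event as well as by grade. Section 6.1.1 also requires source documentation of all adverse events.

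A reader might also take hypoglycemia to be the most likely drug effect. Section 7.2 does not list it and highlights gastrointestinal and retinal effects. The metabolic findings cited come from adults who were obese, insulin resistant or had type 2 diabetes. The protocol's account of them reports no hypoglycemia with the drug.

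Finally, copying the 6.2 exception into 6.1.5 unchanged could turn Stage 2 endpoint glucose values into reportable adverse events and mix efficacy with safety. That objection is sound and shapes the fix.

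What the reply does not remove is Case 1. A non-serious event still has no grade under 6.1.5, while 6.2 requires one.

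**Conclusion.** The inconsistency is real and should be fixed. Its firm consequence is that non-serious hypoglycemia of Grade 2 severity or above may be reported by sites that follow 6.2 and omitted by sites that follow 6.1.5. The between-arm count would then be incomplete to an unknown degree. For serious cases there is a conflict only if the death clause in 6.1.5 is read to cover all three conditions.

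The size cannot be given. The documents contain no hypoglycemia rate, and an assumed incidence would show only that an event of that frequency is likely to occur. It is also tempting to say that the reported number of non-fatal cases would be zero. That would require every site to take the broad reading and to disregard 6.1.3.

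The conclusion assumes that sites work from the protocol text and have no other written instruction on hypoglycemia. The primary endpoint, sample size, error control and interim boundaries are not affected.

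**What to change.** Reconcile 6.1.5 with 6.1.1, 6.1.3 and 6.2 so that one statement governs:

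- Delete hypoglycemia from the exception in 6.1.5, so that it is graded and reported like other adverse events.
- Limit the hyperglycemia exception to glucose findings that constitute or lead to the study endpoint (abnormal glucose tolerance or diabetes), and use the same wording in 6.1.1 and 6.2.
- State that the death-only clause applies to diabetes onset alone.

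No additional SAP table row is needed, because SAP section 8 already summarizes events by system organ class and preferred term. Grade is also an input to the withholding list in 4.5.1, so the sponsor should check that the corrected text and that list remain consistent; this review takes no position on the withholding rule itself. Because source documentation of all adverse events is required, sites can be asked to look back for earlier cases.

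The cost is a short protocol correction, a site notice and some additional adverse event forms.

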### **6.2. Adverse Event Reporting and Monitoring**

Adverse events will be reported to the TrialNet Coordinating Center. The investigator will grade their severity according to common toxicity criteria or study-specific criteria and will make a determination of their relation to therapy *with the exception of the initial diagnosis of diabetes which is considered an adverse event only in the case of death*. Events will be assessed and reported consistent with the ICH Guideline for Good Clinical Practice, 21 CFR 312.32 for expedited safety reporting, and per the guidance of the DHHS Office for Human Research Protections (OHRP).

The adverse event case report form for the protocol must be completed for all AEs  $\geq$  Grade 2. In addition to the reporting requirements for the TrialNet network (as described above), the FDA requires reporting of any adverse event, if the event is serious, related, AND unexpected (21CFR312.32 (c)(i)(A)-(B)). When required, the FDA form 3500A (MedWatch form) should also be completed and sent to the TNCC *within 24 hours of when the site was notified of the event*. This will be reviewed by the TrialNet Medical Monitor, the TrialNet Safety Monitoring Committee, and the DSMB, as appropriate. Deaths must be reported immediately. Event outcome and other follow-up information regarding the treatment and resolution of the event will be obtained and reported when available, if not known at the time the event is initially reported. The follow-up information should contain sufficient detail to allow for a complete medical assessment of the case and an independent determination of possible causality.

Adverse events will be assessed by the TrialNet Medical Monitor. The DSMB will conduct regular safety reviews approximately every three to six months (and otherwise as needed) of adverse events by treatment group assignment. Serious adverse events, as well as adverse events leading to study discontinuation, will be reviewed by the DSMB.

For SAEs that are unexpected and considered possibly or probably drug-related, the Medical Monitor will provide information on frequency of similar events, and will review FDA form 3500A reports for distribution to FDA (and equivalent regulatory bodies for non-US sites), NIDDK, DSMB, and site investigators. Expedited safety reports will be submitted to the IND by the TNCC on behalf of NIDDK.

